11.1.1. Power analysis

We will report post-hoc power analysis when studying the differences in bioavailability between the buccal, IM, and IN formulations of naloxone.

11.2. Randomisation

This study will employ an open-label, within-subject design with repeated sessions. Each participant in stage 1 of the study will receive all five treatment conditions in a random sequence.

Treatment allocation ordering for participants will be in a randomised order, following the randomisation schedule and process as detailed in section 7.5.

As this is an open-label study, there is no blinding involved. Both the investigators and the participants will be aware of the treatment allocation for each session.

11.3. Analysis

At the end of stage 1, AUC₀₋₁₅ of all arms will be computed for making comparisons to decide if further evaluation of IMPs will continue in stage 2. See decision criteria in section 5.4.

All the following analyses will be conducted when the study either terminates at stage 1 or at stage 2. Data will be stratified by stage if the following analysis is conducted at the end of stage 2.

Statistical analysis plan:

Pharmacokinetics parameters:
 Pharmacokinetic parameters (C_{max}, T_{max}, AUC, t_{1/2, T50%}) will be summarized descriptively. Continuous outcomes will be reported as means with standard deviation. Categorical outcomes will be reported as frequencies. Individual participant's

pharmacokinetic data will be presented in tables and graphs. The plasma concentration-time data will be subject to non-compartmental pharmacokinetic analysis using appropriate computer software applications. Linear and log-linear plots will be presented. To assess bioavailability between the formulations, log-transformed AUC and C_{max} observations will be entered into a linear mixed model to account for the repeated measures and between-subject conditions. Linear contrasts representing the difference between conditions will be expressed as a ratio of geometric means along with 95% CI and inference based on p < 0.05.

Protocol violations:

• All protocol violations, including inclusion/exclusion criteria violations and violations during the trial, will be listed, even if they are believed to influence any of the results.

Demographics:

 Demographic and baseline characteristics (including sex, age, BMI, and other relevant parameters) will be summarized using descriptive statistics for the overall study population.

Safety measures:

- Summary tables showing vital signs e.g. body temperature, respiratory rate, pulse rate, and systolic and diastolic blood pressure will be provided at each time point and changes from baseline.
- Individual physical examinations will be listed and summarised at each study time point.
- Important Medical Events, drugs and pregnancy test results during the study will be listed.

Disintegration time

• In vivo disintegration times of the buccal naloxone wafers will be summarized descriptively compared to in vitro data.

Laboratory results:

 Laboratory parameters including haematology, blood chemistry, and urinalysis will be listed accompanied by an indication if the parameter is outside the reference range. A summary of all data outside the reference range of the clinical laboratory will be provided. Clinical laboratory data will be presented descriptively, where applicable.

Adverse events:

A listing of all individual AEs, AR, UAR, SAE, SAR and SUSAR will be provided. Summary tables of the TEAEs will be presented by the system organ class based on the MedDRA terminology list (preferred terms): 1 containing the number of TEAEs (frequency of occurrence, number of participants experiencing the event) by treatment and 1 containing the number of drug related TEAEs (frequency of occurrence, number of participants experiencing the event) per treatment. Additional tables of total counts by treatment and relationship and by treatment and severity will be given.

Missing data handling:

• This study will employ a complete case analysis approach, where only data from participants with full observations for a given endpoint will be included in the primary analysis for that endpoint. However, in the event of early withdrawal, any data already obtained (such as pharmacokinetic and safety data from completed visits) will be retained by the study and may be used in secondary analyses and presented in

publications, where scientifically appropriate. For participants who withdraw after completing at least one but not all experimental visits, their data from completed visits may be included in per-visit analyses.

12. Trial Management Group (TMG)

The TMG will include the Chief Investigator, co-investigators, the statistician, and the trial manager. The TMG will be responsible for overseeing the trial. Since it's a small pharmacokinetic study which is expected to be completed within a few months, we will meet on an ad hoc basis as and when any issues with the trial arise.

The TMG will review recruitment figures, SAEs and substantial amendments to the protocol prior to submission to the REC and/or MHRA.

13. Trial Steering Committee

The Trial Steering Committee (TSC) will provide overall supervision of the trial, ensuring it is conducted according to the protocol and in compliance with Good Clinical Practice (GCP) requirements. The TSC will monitor progress of the trial and recommend any appropriate amendments/actions for the trial as necessary.

For this small Phase 1 pharmacokinetic study with a well-characterized medication, a separate Data Monitoring Committee will not be established. All data monitoring responsibilities will be conducted by the Trial Management Group with oversight from the TSC. The TSC will review safety data after stage 1 before making decisions about progression to stage 2, ensuring appropriate safety monitoring throughout the trial.

14. Direct Access to Source Data and Documents

The Investigator(s) will permit trial-related monitoring, audits, REC review, and regulatory inspections by providing the Sponsors, Regulators and REC direct access to source data and other documents, such as participant consent documents, medical histories, laboratory results, relevant correspondence, and participant guestionnaires.

15. Ethics & Regulatory Approvals

The trial will be conducted in compliance with the principles of the Declaration of Helsinki (1996), the principles of GCP and in accordance with all applicable regulatory requirements including but not limited to the Research Governance Framework and the Medicines for Human Use (Clinical Trial) Regulations 2004, as amended in 2006 and any subsequent amendments.

This protocol and related documents will be submitted for review to Health Research Authority (HRA), REC, and to the Medicines and Healthcare products Regulatory Agency (MHRA) for Clinical Trial Authorisation. Any subsequent protocol amendments will be submitted to the REC, HRA and Regulatory Authorities for approval as appropriate.

Prior to site recruitment the Chief Investigator/Principal Investigator or designee must receive local site approvals e.g. NHS permission in writing from the Trust Research & Development (R&D) known as confirmation of capability and capacity.

The Chief Investigator will submit a final report at conclusion of the trial to the KHP-CTO (on behalf of the Sponsor) and the REC within the timelines defined in the Regulations. The KHP-CTO or delegate will upload the final report to a publicly registered database on behalf of the Sponsor.

16. Quality Assurance

This is a small pharmacokinetic study with a short duration and short follow-up where the majority of outcome data will not be available until after laboratory analysis. The benefits of data audit are therefore limited. Data will be made available for inspection and monitoring by relevant authorities on request.

Monitoring of this trial will be to ensure compliance with Good Clinical Practice and scientific integrity will be managed and oversight retained, by the KHP-CTO Quality Team.

17. Data Management

The study will adhere to KCL's policy on data management, security and sharing. Participants will provide mobile phone numbers so that we can contact them during the study. If a participant requests, they will be contacted with the study outcome.

The Chief Investigator will act as custodian for the study data and all participant data will be pseudo-anonymised.

- All pseudo-anonymised data will be stored on a password-protected computer.
- Data will be collected using source data worksheets (paper questionnaires).
- Each study participant will be given a study ID.
- Source documents will be named with this ID.
- The source documents will be kept in locked cabinets. Study data will be transcribed to the Elsevier MACRO EDC system.
- All data will have restricted access with full audit trails for all activity

All shared research data will undergo pseudo-anonymization following ICH-GCP guidelines, with personal identifiers replaced by unique study ID. The primary research data available for sharing will include pseudo-anonymized pharmacokinetic data, non-identifiable demographic information, clinical observations, safety and tolerability measurements, and laboratory results, all documented in a standardized format suitable for future analysis Any personal data collected, will be stored and accessible for over 3 years after the study has ended. Research data generated by the study will be stored for 25 years.

All trial data will be stored in line with the Medicines for Human Use (Clinical Trials) Amended Regulations 2006 and the Data Protection Act and archived in line with the Medicines for Human Use (Clinical Trials) Amended Regulations 2006 as defined in the KHP-CTO Archiving Standard Operating Procedure (SOP). Regular backups of data will be made, retaining more than one copy of data.

All essential documents relating to the clinical study must be archived in accordance with the KHP-CTO SOP and the requirements of the UK Regulations as follows:

- Site Documentation: For at least 25 years after the completion of a clinical study, as defined by the Regulations.
- ➤ Trial Master File and all Essential Documentation: For a minimum of 25 years or until at least 2 years after the last approval of a marketing application in a region where the ICH guideline applies.

Data resulting from this study will be reported and disseminated at international conferences, in peer-reviewed scientific journals, publications on website and submission to regulatory authorities. Where appropriate, the results will be disseminated to the general public by means of press releases, posts on social media and at public engagement events; in all cases, data will be non-identifiable and individual participants will not be identifiable in publications.

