5.1. Trial Objectives

Primary Objective

1. To characterize and compare the pharmacokinetic profile of a novel buccal formulation of naloxone in healthy volunteers with approved formulations (naloxone ampoule) as the injectable form, and Nyxoid[®] as naloxone nasal spray comparison.

Secondary Objectives

- 1. To measure the dose-proportionality of the novel formulation by comparing the plasma exposure of two different buccal doses and one sublingually.
- 2. To assess the safety and tolerability of the novel buccal formulation

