7.5. Randomisation Procedure / Code Break

This study will employ an open-label, within-subject design with repeated sessions. Each participant in stage 1 of the study will receive all five treatment conditions in a random sequence. A randomisation schedule will be created using five treatment conditions with a corresponding code as per Table 2.

Table 4 Treatment Coding for Randomisation

Treatment Code:	Drug administration and dosage	IMP/Comparator
Α	Buccal administration of 2mg naloxone rapid dispersal wafer	IMP
В	Buccal administration of 4mg naloxone (2x 2mg) rapid dispersal wafers	IMP
С	Sublingual administration of 2mg naloxone rapid dispersal wafer	IMP
D	IM administration of 0.4mg/1ml naloxone ampoule	Comparator
E	IN administration of 1.8m/0.1ml naloxone (Nyxoid®)	Comparator

Another randomisation schedule will be created accordingly for stage 2 of the study if the study does not terminate early (i.e., when at least one of the IMPs is selected for further evaluation)

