9.2. Procedures for Assessing Efficacy Parameters

The following procedures will be used to assess the efficacy parameters:

Blood Sampling:

- Venous blood samples (1 mL) will be collected via IV cannulation at the following time points for each formulation: 0 (pre-dose), 2, 4, 6, 8, 10, 12.5, 15, 30 and 45 minutes and 1, 1.5, 2, 4 hours after dosing. Each sample will be split into two plasma cryovials.
- Samples will be centrifuged within 30 minutes of collection, and plasma will be separated and stored at -20°C until the end of the visit, and then stored at -80°C until analysis.

Plasma Naloxone Analysis:

- Plasma concentrations of naloxone will be determined using a validated liquid chromatography-tandem mass spectrometry (LC-MS/MS) method.
- The following parameter will be recorded in the eCRF for each time point: plasma naloxone concentration (ng/mL).

Pharmacokinetic Analysis:

- AUC will be calculated using the linear trapezoidal method and extrapolated to infinity.
- C_{max} and T_{max} will be determined directly from the observed concentration-time data.
- t1/2 will be calculated using the terminal elimination rate constant.
- Relative bioavailability will be calculated by comparing the dose-normalized AUC0-∞ of buccal and sublingual naloxone to that of IM and IN formulations.

Buccal and Sublingual Wafer Disintegration:

- The time for complete disintegration of the buccal naloxone wafer will be measured and recorded by a study team member.
- Participants will be asked to report the moment they feel the wafer has completely disintegrated.
- The following will be recorded in the CRF: time to complete disintegration (seconds).

Visual Analogue Scale (VAS) for Taste and Tolerability:

- Participants will complete a 100mm VAS immediately after administration of each formulation to assess taste and local tolerability.
- The following will be recorded in the CRF: VAS score for taste (0-100), VAS score for tolerability (0-100).

All efficacy assessments will be conducted for each of the three formulations (buccal/sublingual, IM, and IN) and for each dose of the buccal formulation (2mg and 4mg). The data collected will be used to construct individual plasma concentration-time profiles, calculate pharmacokinetic parameters, and compare the efficacy of the buccal and sublingual naloxone formulation to the existing IM and IN formulations.

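### The bioavailability model in section 11.3 names no dose-normalisation, although section 9.2 dose-normalises relative bioavailability and the wafers carry 5 or 10 times the IM dose

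*Protocol*

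**What the plan says.** Section 11.3, under its own label of statistical analysis plan, states one inferential model for the pharmacokinetic data: "To assess bioavailability between the formulations, log-transformed AUC and C_{max} observations will be entered into a linear mixed model". The contrasts between conditions are to be "expressed as a ratio of geometric means along with 95% CI and inference based on p < 0.05". The section mentions no dose-normalisation and no dose term. It states no null ratio, and testing a difference between conditions implies 1. It does not say whether AUC means the first 15 minutes or the extrapolation to infinity.

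Section 9.2 defines the quantity differently: "Relative bioavailability will be calculated by comparing the dose-normalized AUC0-∞ of buccal and sublingual naloxone to that of IM and IN formulations". It does not mention normalising Cmax or the AUC over the first 15 minutes.

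The doses are in Table 4 of section 7.5. The two buccal arms are "Buccal administration of 2mg naloxone rapid dispersal wafer" and "Buccal administration of 4mg naloxone (2x 2mg) rapid dispersal wafers". The others are 2 mg sublingual, 0.4 mg IM and 1.8 mg IN. For the IN product, section 6.1 gives 1.8 mg as the hydrochloride dihydrate and also a 2 mg hydrochloride equivalent.

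Secondary objective 1 in section 5.1 reads: "To measure the dose-proportionality of the novel formulation by comparing the plasma exposure of two different buccal doses and one sublingually". Section 11.3 names no analysis for it.

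**The concern.** The model is assigned to bioavailability, but it is fitted to arms whose doses span a factor of ten. Without normalisation, a contrast on the log scale mixes relative bioavailability with the dose ratio, and a ratio of 1 is then the wrong reference value for bioavailability against IM. Two wrong statements could follow. A poorly absorbed wafer could be reported as not differing from IM in bioavailability only because it carries more drug. A wafer absorbed as completely per mg as IM would be reported as significantly different. Section 11.1.1 plans a post-hoc power analysis for differences in bioavailability, and it would inherit the same ambiguity.

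Dose-proportionality is exposed in the same way. If the listed contrasts are the only ones produced, a reader may hold the 4 mg to 2 mg buccal ratio against 1, although proportionality predicts 2. The sublingual arm, listed under this objective, repeats the 2 mg dose by another route and adds no dose level.

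**Working it through.** **The plan's own figure.** The protocol gives no power, effect size or variability for this model. The only related number is the stage 1 size in section 11.1: 12 completers with 20% drop-out gives 12 / (1 − 0.20) = 15 randomised, which agrees with the text. The value n = 12 is used below.

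**Step 1: what a raw contrast estimates.** Raw ratio of geometric means = (dose ratio) × (relative bioavailability per mg). The relative bioavailability that corresponds to a raw ratio of 1 is therefore 1 / (dose ratio). This step needs no assumption about variability.

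| Contrast | Dose ratio = raw ratio if bioavailability per mg is equal | Relative bioavailability at raw ratio 1 |
|---|---|---|
| 2 mg wafer / IM | 2 / 0.4 = 5 | 20% |
| 4 mg wafer / IM | 4 / 0.4 = 10 | 10% |
| 2 mg wafer / IN | 2 / 1.8 = 1.11, or 2 / 2 = 1 | 90% or 100% |
| 4 mg wafer / IN | 4 / 1.8 = 2.22, or 4 / 2 = 2 | 45% or 50% |
| 4 mg / 2 mg buccal | 4 / 2 = 2 | 50% |
| 2 mg buccal / 2 mg sublingual | 2 / 2 = 1 | 100% |

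**Step 2: how often a raw test against 1 would reject when bioavailability per mg is equal.** Here a within-subject CV has to be assumed; 20% to 100% was used. SE of the log ratio = √(2 ln(1 + CV²) / n), with n = 12, five periods and (11 × 4) − 4 = 40 degrees of freedom, referred to the noncentral t distribution. Example for 4 mg versus 2 mg at CV 50%: SE = √(2 × 0.2231 / 12) = 0.193, and ln 2 / 0.193 = 3.59, which gives 94%.

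- 2 mg wafer versus IM: at least 99.6% over the whole CV range.
- 4 mg wafer versus IM: about 100%.
- 4 mg versus 2 mg buccal: about 100% at CV 30%, 94% at 50%, 65% at 80% and 51% at 100%.

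If the trial goes on to stage 2, the sample is larger. With 30 participants, and five periods kept for illustration, the last figure rises from 51% to 89%.

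**Step 3: what normalising changes.** Dividing by dose subtracts a constant, ln(dose ratio), from each log contrast. The SE and the relative width of the interval stay the same. The estimate, the position of the interval and the p-value against 1 move. One simulated 12-participant, five-treatment crossover (CV 50%, equal bioavailability per mg) shows this, with an SE of 0.184 throughout:

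- 2 mg buccal / IM: raw 4.50 (95% CI 3.10 to 6.51), p = 2 × 10⁻¹⁰; normalised 0.90 (0.62 to 1.30), p = 0.57.
- 4 mg / 2 mg buccal: raw 1.99 (1.38 to 2.89), p = 0.0005; normalised 1.00 (0.69 to 1.44), p = 0.98.

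**The case against.** The strongest reply is that the two sections can be read together: 9.2 defines the quantity, 11.3 supplies the model, and a separate analysis plan may name the exact response variable. Part of this stands. Section 11.3 is silent on normalisation and nowhere states that raw data will be used. A reader might infer an outright contradiction, but the documents show a mismatch by omission. Leaving the matter to a separate plan does not settle it, because 11.3 itself fixes the response variables, the contrasts, the significance rule and their stated purpose.

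Other limits also stand:

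- A reader might extend the mismatch to Cmax and early AUC. Section 9.2 normalises only AUC to infinity, so no conflict exists there.
- A reader might say that the contrasts test dose and carry no information on bioavailability. That is too strong. The dose factor is a known constant, so bioavailability can be recovered from the same fit.
- Raw exposure against IM is a legitimate comparison for the primary objective, and the stage 1 rule in section 5.4 compares early AUC at the administered doses. Only the label of bioavailability is at fault.
- The harm against IM would also require the dose-normalised comparison promised in 9.2 to be left out or overlooked.
- A reader might infer that the protocol plans to test proportionality against a ratio of 1. Section 11.3 assigns no such test. The rejection probabilities show what would happen if the contrast were read that way, and they depend on assumed CVs.
- The model is said "to account for the repeated measures and between-subject conditions", which a reader might call a plain error in a crossover. The wording is loose, but the analysis is stratified by stage and the stages enrol different people, so stage is a between-subject factor. The lack of a named period effect is detail that a protocol may leave to the analysis plan.

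**Conclusion.** The point holds as an inconsistency between sections 9.2 and 11.3. Followed literally, the 11.3 contrasts against IM answer an exposure question while being assigned to bioavailability, with a displacement of a factor of 5 for 2 mg and 10 for 4 mg. Against IN the 4 mg contrast is displaced by a factor of 2 to 2.22 and the 2 mg contrast by at most 11%. Buccal against sublingual at 2 mg is not displaced. For proportionality the displacement is a factor of 2, and it matters only if the raw contrast is read against 1.

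These factors follow from the stated doses alone. Only the rejection probabilities rest on assumed CVs, on n = 12 and on a null ratio of 1, which the protocol implies but does not state.

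This is a should-fix. The primary endpoint is Tmax, relative bioavailability is not among the endpoints in sections 5.2 and 5.3, the stage 1 selection rule does not use this model, and no data would be lost.

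**What to change.** Amend section 11.3 as follows:

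- For relative bioavailability against IM and IN, model the log of dose-normalised AUC to infinity, in line with section 9.2.
- State the dose and salt basis used to normalise each product. For IN, section 6.1 gives both 1.8 mg and a 2 mg equivalent, and the analysis needs one stated basis.
- Keep the un-normalised AUC and Cmax contrasts, say which AUC is meant, and label them exposure comparisons at the administered doses.
- Assess dose-proportionality by the dose-normalised buccal 4 mg to 2 mg geometric mean ratio with its confidence interval around 1. Report sublingual against buccal at 2 mg as a separate route contrast.

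The cost is a few sentences and one derived variable. No sampling, visit or sample size changes. It is best settled before stage 1 concentrations are seen, because the trial is open-label.

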7.6. Withdrawal of Participants

- i. Withdrawal of consent.
- ii. Significant abnormalities detected during the medical assessment or blood tests at the screening visit.
- iii. Suspected Unexpected Serious Adverse Reaction.
- iv. Participant does not attend follow-up point.
- v. Investigator discretion.

Session-specific exclusions:

If a participant meets any of the following session-specific exclusion criteria, the session will be postponed and rescheduled for a later date. The participant will remain enrolled in the study and can complete the remaining sessions as planned, provided they meet all criteria at the time of the rescheduled session.

- i. Use of any over-the-counter medications containing codeine or other opioids, prescribed opioid medication or of illicitly obtained opioids within the past 2 weeks (if the participant is taking a long-acting opioid the period might, after consideration by the examining doctor, be extended to 4 weeks or longer according to washout period).
- ii. Urine drug screen positive for any substance on the day of the session.
- iii. Positive alcohol breath test (above 0) on the day of the session.
- iv. Presence of any acute respiratory symptoms (such as cough, shortness of breath, sore throat), suspected/confirmed COVID-19, other respiratory infection or any other acute disease at the investigator's discretion.

Participants have the right to withdraw from the study at any time for any reason. The investigator also has the right to withdraw participants from the study drug in the event of intercurrent illness, AEs, SAEs, SUSARs, protocol violations, administrative reasons, or other reasons. It is understood by all concerned that an excessive rate of withdrawals can render the study un-interpretable; therefore, unnecessary withdrawal of participants should be avoided. Should a participant decide to withdraw from the study, all efforts will be made to report the reason for withdrawal as thoroughly as possible.

If participants are withdrawn prior to completing all five experimental visits and are therefore missing a full dataset from experimental visits, they will be replaced. Participants lost to follow-up will not be replaced.

In the event of early withdrawal, any data already obtained, such as pharmacokinetic and safety, can be retained by the study and may be used in analyses and presented in publications.

Withdrawal Due to Missed Visits:

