Since this is a 5-way crossover requiring all treatments for analysis, missing 2 consecutive scheduled visits or 3 total visits should constitute withdrawal, as incomplete data would compromise the crossover design.

Lost to follow up:

For contact attempts before classifying participants as lost to follow-up we would make three contact attempts over a one-week period using multiple communication methods including phone calls, emails, and text messages if participants have consented to receive them. These

attempts should be spaced at 24 hours, three days, and seven days after a missed appointment, with each attempt using a different contact method when possible. All contact attempts should be thoroughly documented in the source documents, and participants should be classified as lost to follow-up only after all three attempts have failed to elicit any response.

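### Section 11.3 names a mixed model for log AUC and log Cmax but limits the primary analysis to participants with full observations, which leaves out usable visits at a moderate cost in precision.

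*Protocol*

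**What the plan says.** Four parts of the protocol bear on this.

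- **Model (11.3).** Log-transformed AUC and Cmax "observations will be entered into a linear mixed model to account for the repeated measures and between-subject conditions". Contrasts between conditions are reported as ratios of geometric means with 95% confidence intervals.
- **Missing data (11.3).** The approach is complete case: "only data from participants with full observations for a given endpoint will be included in the primary analysis for that endpoint". Data from the completed visits of participants who withdraw early "will be retained by the study and may be used in secondary analyses and presented in" publications, and for those who withdraw after at least one visit, "their data from completed visits may be included in per-visit analyses".
- **Withdrawal and replacement (7.6).** Replacement applies "If participants are withdrawn prior to completing all five experimental visits". For missed visits, "missing 2 consecutive scheduled visits or 3 total visits should constitute withdrawal"; the reason given is that the five-way crossover needs every treatment for its analysis. Sessions that fail the session-specific criteria are postponed and rescheduled.
- **Numbers (11.1).** Stage 1 selection uses complete data from 12 participants, with five responses each. The expected drop-out is 20%, so 15 are to be randomised. Stage 2 recruits 30-35. There is no formal sample size calculation.

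**The concern.** A mixed model with a participant effect does not need every participant to have every treatment. It uses each evaluable visit, and its estimates are valid if the missing values are missing at random. The complete-case rule removes that advantage: a participant with four good profiles contributes nothing to the main AUC or Cmax comparison. The premise in 7.6, that all treatments are required for analysis, does not hold for the model named in 11.3.

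The replacement rule does not fully make up for this. Someone who misses one visit, or two visits that are not consecutive, is not withdrawn on that ground. Someone who attends all five visits but loses one profile is not withdrawn either. Both are excluded from the primary analysis, and neither is assured of replacement.

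Precision in a small trial is at stake and, under some mechanisms, bias. The protocol states the rule itself, so a statistical analysis plan that used all visits would contradict it.

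**Working it through.** **Step 1. What full observations means.** The phrase could refer to the samples within one visit. Section 11.1 defines complete data as five responses per participant, one per arm; 7.6 speaks of needing all treatments; and the next sentence of the missing-data rule contrasts complete participants with those who withdraw. The natural reading is all visits.

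**Step 2. The plan's own figure.** 12 / (1 − 0.20) = 15 randomised. This reproduces 11.1 exactly and leaves 3 of 15 incomplete.

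**Step 3. Visits left out.** If each of the 3 incomplete participants has k evaluable visits, 60 + 3k visits are obtained and 3k of them are excluded.

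**Step 4. Effect on precision.** The inputs from the protocol are five treatments, five periods, random sequences, 12 complete and 3 incomplete. The protocol gives no standard deviation or within-participant correlation ρ, so ρ was assumed to lie between 0.3 and 0.9. For participant i with visit design matrix X_i (treatment and period effects), V_i = (1 − ρ)I + ρJ, where J is a matrix of ones. The covariance of the estimates is (Σ X_i′ V_i⁻¹ X_i)⁻¹. The variance of a treatment contrast was averaged over all pairs of treatments and over 300 random layouts, for the 12 completers alone and for all 15. Incomplete participants keep their first k visits.

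| Visits per incomplete participant (k) | Visits excluded | Variance, complete-case / all visits | Interval width ratio |
|---|---|---|---|
| 4 | 12 of 72 (16.7%) | 1.204-1.211 | about 1.10 |
| 3 | 9 of 69 (13.0%) | 1.134-1.147 | about 1.07 |
| 2 | 6 of 66 (9.1%) | 1.066-1.089 | 1.03-1.04 |
| 1 | 3 of 63 (4.8%) | 1.006-1.038 | 1.00-1.02 |

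The ranges run over ρ. The width ratio is the square root of the variance ratio and ignores the small change in degrees of freedom.

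*Check by hand.* A participant with k visits gives k − 1 within-participant comparisons. Twelve completers give 12 × 4 = 48. Three more with four visits add 3 × 3 = 9, and 57 / 48 = 1.19. With three visits, 54 / 48 = 1.13; with two, 51 / 48 = 1.06; with one, 48 / 48 = 1.00. These agree closely with the table at high correlation.

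**Step 5. If visits are lost singly.** Suppose each visit independently loses the endpoint with probability p (assumed), with no replacement. The expected number complete of 15 is 15(1 − p)⁵. The share of obtained visits excluded is 1 − (1 − p)⁴.

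| p | Complete of 15 | Share of obtained visits excluded |
|---|---|---|
| 2% | 15 × 0.904 = 13.6 | 7.8% |
| 4.4% | 15 × 0.799 = 12.0 | 16.5% |
| 5% | 15 × 0.774 = 11.6 | 18.5% |
| 10% | 15 × 0.590 = 8.9 | 34.4% |

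The 4.4% row matches the planned 20% incomplete. The 10% row implies 41% incomplete, about twice the planned figure, and is an extreme case.

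**The case against.** The case for leaving the rule alone has real substance.

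- **The target is already complete data.** The figure of 12 is the number with all five responses, not the number enrolled. A reader might apply loss rates to 12 and conclude that Stage 1 shrinks to 11, 9 or 7 people. Section 11.1 does not support that, because 15 are randomised to allow for the loss.
- **Losses may be fewer.** Postponement under 7.6 will recover some sessions. The investigator may also withdraw a participant for administrative or other reasons, which would trigger replacement after one unrecoverable visit. Replacement is therefore not assured, rather than impossible.
- **The data are not thrown away.** Completed visits of withdrawn participants may enter secondary or per-visit analyses. That stands, but the provision is optional and worded for withdrawals.
- **The primary endpoint is not in conflict with the model.** A reader might infer that the primary comparison of the trial is affected. Tmax is summarised descriptively (5.2, 11.3), and no paired test of Tmax or T50% is specified. The mismatch concerns AUC and Cmax, which are secondary endpoints, although AUC0-15 also drives Stage 1 selection.
- **Bias is not demonstrated.** If loss depends only on stable participant characteristics, within-participant contrasts among completers remain unbiased under an additive model. If it depends on the unobserved value at the missed visit, the mixed model is biased too. What remains is loss driven by earlier observed responses. Withdrawal for adverse events makes that conceivable, but the protocol gives no evidence for it.

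These points limit the size and reach of the concern. They do not supply a reason to exclude evaluable visits from a model that can use them.

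**Conclusion.** The point holds for the AUC and Cmax mixed model. Following 11.3 as written excludes usable visits from the main comparison, and the replacement rule does not assure that the number of completers is restored. At the planned 3 of 15 incomplete, the complete-case variance is about 1.01 to 1.21 times the all-visits variance, so intervals are up to about 10% wider. This result hardly depends on the assumed correlation. It depends mainly on how many visits the incomplete participants have, which the protocol cannot tell us.

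Complete-case estimates could also be biased if exclusion depends on earlier observed responses. A mixed model on all visits handles that case, but not loss that depends on unobserved values.

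If Stage 1 recruits until 12 are complete, the count is protected, but the excluded visits and any selection remain. In Stage 2 the same logic applies, with up to the number of arms minus one visits excluded per incomplete participant; that number is not yet fixed. This is a moderate, cheaply corrected loss and does not invalidate the trial.

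**What to change.** In 11.3, replace the complete-case rule for log AUC (including AUC0-15) and log Cmax: the main mixed model uses all evaluable visits from all randomised participants, and the complete-case analysis becomes a sensitivity analysis. State the missing-at-random assumption on which the model then relies.

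Decide whether the Stage 1 AUC0-15 ratio in 5.4 follows the same rule. If it does, align the wording in 11.1 on complete data from 12 participants and the statement in 7.6 that all treatments are required for analysis. The withdrawal and replacement rules themselves need not change for this purpose. Tmax and T50% need no new instruction here, because no model or paired test is specified for them.

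The cost is a paragraph in 11.3 and, if Stage 1 selection is included, small wording changes in 11.1 and 7.6. No further data or participants are needed. Settle it before Stage 1 data are seen, because the study is open-label and the present wording leaves the use of incomplete data to discretion.
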